7.2.1.4. Systemic Events

Prior to vaccination, subjects will consider whether they generally experience fatigue, headache, muscle pain, or joint pain. If so, the symptoms will be graded as mild, moderate, or severe and recorded in the e-diary as baseline symptoms. The Systemic Event Grading Scale in Table 10 will be used.

Starting on the day of vaccination, and for 10 consecutive days, postvaccination systemic events will be assessed by the subject each day, and if present, they will be graded as mild, moderate, or severe and recorded in the e-diary, using the grading scale in Table 10.

A subject with a severe/Grade 3 systemic event will be instructed to contact the investigator who will assess the reaction. In the event that the subject does not call, the investigator will call the subject.

7.2.1.4.1. Management of Grade 4 Systemic Events

Only an investigator is able to classify a subject's systemic event as Grade 4, after physical examination of the subject or telephone contact with the subject. Confirmed Grade 4 systemic events require immediate notification to the sponsor and include:

- An emergency room visit for management of a systemic event:

Consider whether the systemic event is an important medical event ([Section 8.6](#)). If yes, report the event as an SAE; if no, report it as an AE. Grade the severity of the systemic event using the AE severity grading scale in [Section 8.8](#).

- Hospitalization for management of a systemic event:

Report hospitalizations for management of a systemic event as an SAE and grade the severity of the systemic event according to the AE severity grading scale in [Section 8.8](#).

Table 10. Systemic Event Grading Scale

	GRADE 1 mild	GRADE 2 moderate	GRADE 3^a severe	GRADE 4^b
Fatigue (Tiredness)	Does not interfere with activity	Some interference with activity	Prevents daily routine activity	Emergency room visit or hospitalization
Headache	Does not interfere with activity	Some interference with activity	Prevents daily routine activity	Emergency room visit or hospitalization
Vomiting	1 to 2 times in 24 hours	>2 times in 24 hours	Requires intravenous hydration	Emergency room visit or hospitalization
Diarrhea	2 to 3 loose stools in 24 hours	4 to 5 loose stools in 24 hours	6 or more loose stools in 24 hours	Emergency room visit or hospitalization
Muscle pain	Does not interfere with activity	Some interference with activity	Prevents daily routine activity	Emergency room visit or hospitalization
Joint pain	Does not interfere with activity	Some interference with activity	Prevents daily routine activity	Emergency room visit or hospitalization

Abbreviations: AE = adverse event; CRF = case report form.

- a. Subjects experiencing severe systemic events will telephone the study site. In the event that the subject does not call, the investigator will call the subject.
- b. Grade 4 assessment should be made by the investigator and recorded as an AE on the CRF. Manage as shown in [Section 7.2.1.4.1](#) and [Section 8.8](#).

7.2.1.5. Fever

To record fever, a digital thermometer will be given to the subject with instructions on how to measure his or her oral temperature. Starting on the day of vaccination, temperature will be measured each evening for 10 consecutive days and at any time during the 10 days that fever is suspected. Fever is defined as an oral temperature of $\geq 38.0^{\circ}\text{C}$ (100.4°F). The highest temperature for each day will be recorded in the e-diary. In the event of a fever, temperature will be collected daily until fever has resolved (1 day with a temperature less than 38.0°C [100.4°F]). Temperature will be measured and recorded to 1 decimal place and then categorized during analysis according to the scale shown in Table 11.

Where a fever $\geq 39.0^{\circ}\text{C}$ ($\geq 102.1^{\circ}\text{F}$) is recorded, the subject will contact the investigator by telephone and the investigator will assess whether a severe local reaction or fever assessment visit is required (refer to [Section 6.4.1.1.1](#)). If the subject does not call the investigator, the investigator will contact the subject.

Table 11. Scale for Fever

38.0 to 38.4°C (100.4 to 101.1°F)
38.5 to 38.9°C (101.2 to 102.0°F)
39.0 to 40.0°C (102.1 to 104.0°F)
>40.0°C (>104.0°F)

7.2.2. Preoperative and Perioperative Subject Status Assessments

7.2.2.1. Charlson Comorbidity Index

The Charlson comorbidity index (CCI) is a validated prognostic indicator for which factors, individually or in combination, may increase the risk of short-term mortality for patients enrolled in longitudinal studies.⁵⁵ On completion of the physical examination at Visit 1, the investigator or designee will record the presence of each comorbid condition and age cohort as presented in Table 12 in the CRF.

The sum of the values for each comorbid condition is added to the subject's value for age to obtain the CCI. Both the CCI and the Charlson probability (10-year survival) will be derived programmatically.

CCI = sum of comorbid conditions + value for age (on the date of assessment)

Table 12. Charlson Comorbidity Score

Comorbid Condition	Score	Age Cohort and Value for Age (on the Date of Assessment)
History of prior myocardial infarction (not ECG changes only)	1	Age ≤40 years: 0 points
Congestive heart failure	1	Age 41-50 years: 1 point
Peripheral vascular disease	1	Age 51-60 years: 2 points
Cerebrovascular disease	1	Age 61-70 years: 3 points
Dementia	1	Age 71-80 years: 4 points
Diabetes	1	Age 81-90 years: 5 points
Mild liver disease	1	
Chronic pulmonary disease	1	
Gastric/duodenal ulcer	1	
Connective tissue disease	1	
Hemiplegia	2	
Moderate or severe renal disease	2	
Diabetes with end-organ damage	2	
Tumor	2	
Leukemia	2	
Lymphoma	2	
Moderate or severe liver disease	3	
Metastatic solid tumor	6	
AIDS	6	

Abbreviations: AIDS = acquired immunodeficiency syndrome; ECG = electrocardiographic.

7.2.2.2. American Society of Anesthesiologists (ASA) Physical Status Classification Score

The American Society of Anesthesiologists (ASA) physical status classification system is utilized by anesthesiologists to assess the fitness of surgical patients prior to undergoing surgery. ASA scores correlate with patient morbidity and postoperative infection risk.⁵⁶ At Visit 2 and prior to surgery, the subject's physical status will be assessed and classified by the anesthesiologist using the ASA score shown in Table 13.

Table 13. American Society of Anesthesiologists (ASA) Physical Status Classification

Score	Description
1	Healthy patient
2	Mild systemic disease with no functional limitation
3	Severe systemic disease with definite functional limitation
4	Severe systemic disease that is a constant threat to life
5	Moribund patient unlikely to survive 24 hours with or without operation

Adapted from American Society of Anesthesiologists. ASA physical status classification system. Available: <http://www.asahq.org/Home/For-Members/Clinical-Information/ASA-Physical-Status-Classification-System>. 18 Jun 2014.

7.2.3. Assessment of Organ Failure

All subjects who undergo the index surgical procedure will be monitored for OF events across the following time periods:

- during the index hospital admission from after surgery until discharge
- during any subsequent hospitalization(s) that occur over the course of the study including, where possible, those that occur at any outside hospital

As OF is sequential and progressive, subject monitoring will occur on a daily basis while the subject is hospitalized. There is no protocol requirement to perform the procedures required to calculate a daily SOFA score; rather, the investigator will review the subject's clinical care records (eg, laboratory results, nursing and medical progress notes) to determine whether or not the subject meets the criteria for an OF event. If the data required to score an organ are not available on the day of assessment, by default the score for that variable will be zero (0).

A clinical diagnosis of organ failure will be established for each of the 6 organ systems—respiratory, cardiovascular, renal, hematological, neurological, and hepatic—on the basis of SOFA scores⁵⁷ (Table 14). OF is defined as a SOFA score ≥ 3 in any 1 organ system, while MOF is defined as OF in 2 or more organ systems simultaneously.

If the subject develops organ system dysfunction, daily SOFA scores are recorded on the SOFA worksheet until organ function returns to normal/baseline or until hospital discharge if the event remains unresolved.

When a SOFA score of ≥ 3 (OF) is recorded for any single organ, SOFA scores will be entered into the CRF on a daily basis until the failing organ system(s) returns to normal/baseline or stabilizes.

Organ dysfunction and OF events will be reported as AEs or SAEs as appropriate.

All MOF events will be adjudicated by the EAC to determine whether the protocol-defined clinical criteria have been met, whether confirmed events are PDI related or due to noninfectious causes, and whether the PDI-related events are attributable to

microbiologically confirmed *S aureus*, attributable to other organism(s), or without microbiological confirmation.

Additional guidance for obtaining and reporting the SOFA scores and reporting MOF is provided in the SRM.

Table 14. Sequential Organ Failure Assessment Score

Variables	SOFA Score				
	0	1	2	3	4
Respiratory PaO ₂ /FiO ₂ , mm Hg or SpO ₂ /FiO ₂ , mm Hg ^a	>400	≤400	≤300	≤200 ^b	≤100 ^b
Coagulation Platelets x 10 ³ /μL	>150	≤150	≤100	≤50	≤20
Liver Bilirubin, mg/dL	<1.2	1.2-1.9	2.0-5.9	6.0-11.9	≥12
Cardiovascular Hypotension	No hypotension	Mean arterial pressure <70 mm Hg	Dop ≤5 or dob (any dose) ^c	Dop >5, epi ≤0.1, or norepi ≤0.1 or phenylephrine ≤0.1 ^c ; or vasopressin <0.04 U/min	Dop >15 epi >0.1, or norepi >0.1 or phenylephrine >0.1 ^c ; or vasopressin ≥0.04 U/min
Central nervous system Glasgow Coma Scale (GCS) score ^d	15	13-14	10-12	6-9	<6
Renal Creatinine, mg/dL or urine output, mL/d	<1.2	1.2-1.9	2.0-3.4	3.5-4.9 or <500	>5 or <200 ^e

Abbreviations: dob = dobutamine; Dop = dopamine; epi = epinephrine; FiO₂ = fraction of inspired oxygen; norepi = norepinephrine; PaO₂ = partial pressure of oxygen in arterial blood; SOFA = Sequential Organ Failure Assessment; SpO₂ = saturation of peripheral oxygen.

- The preferred measurement for the assessment of respiratory failure is the partial pressure of oxygen in arterial blood (PaO₂) from arterial blood gas data. If that is unavailable, respiratory failure may also be evaluated using a modified respiratory SOFA score based on saturation of peripheral oxygen (SpO₂) and available FiO₂ measurements (eg, face mask, bilevel positive airway pressure, continuous positive airway pressure).⁵⁸ If the direct FiO₂ measurement is not available (eg, nasal cannula), a respiratory score should not be calculated.
- Values are with respiratory support.
- Adrenergic agents administered for at least 1 hour (doses given are in μg/kg per minute).
- In patients receiving sedation or muscle relaxants, normal brain function will be assumed for neurological assessment unless there is evidence of altered mentation.
- Or patient is receiving intermittent hemodialysis, peritoneal dialysis, or continuous renal replacement therapy.

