### 6.2.2. Multiple-Organ Failures

Each multiple-organ failure (MOF) will be classified as an AE or SAE and so appear in the appropriate analysis. However, other MOF endpoints will also be examined:

- Number and proportion of subjects with organ system failure by organ (eg, renal, hepatic, pulmonary). By definition of MOF, each subject will be included in analyses of more than 1 organ.
- Number and proportion of subjects who meet the criteria for MOF.
- Among subjects with MOF, the number and proportion associated with PDI, non-PDI (other infection), other (not an infection), or unknown. More than 1 category may be selected.
- Among subjects with MOF that is associated with PDI or non-PDI, whether the infection is microbiologically confirmed *S aureus*, microbiologically confirmed non-*S aureus*, or not microbiologically confirmed.

Statistical methodology for MOF is described in [Section 8.1.2.2](#).

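### Table 14 uses one set of cut-offs for PaO2/FiO2 and SpO2/FiO2, so a subject validly scored by SpO2 at FiO2 of 0.50 or more always reaches organ failure, while some hypoxaemic subjects are under-scored

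*Protocol*

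**What the plan says.** Protocol 7.2.3, Table 14, labels its respiratory row "PaO ₂ /FiO ₂ , mm Hg or SpO ₂ /FiO ₂ , mm Hg". The row has one set of cut-offs: >400 (score 0), ≤400 (1), ≤300 (2), ≤200 (3) and ≤100 (4).

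Three conditions govern its use:
- Footnote a gives an order of measurement: "The preferred measurement for the assessment of respiratory failure is the partial pressure of oxygen in arterial blood". If that is unavailable, "respiratory failure may also be evaluated using a modified respiratory SOFA score based on saturation of peripheral oxygen", with reference 58 cited for the modified score.
- Footnote a also withholds a respiratory score when FiO2 is not directly measured, as with a nasal cannula.
- Footnote b, attached to scores 3 and 4, reads "Values are with respiratory support". The protocol does not say what counts as support.

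Section 7.2.3 then states that "OF is defined as a SOFA score ≥ 3 in any 1 organ system". The rule for multiple-organ failure comes next in the same sentence and builds on it: "while MOF is defined as OF in 2 or more organ systems simultaneously". The section requires no tests to be done for scoring, sets an organ with missing data to zero, sends MOF events to the adjudication committee (EAC), and refers to the study reference manual (SRM) for further guidance.

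SAP 6.2.2 lists "Number and proportion of subjects who meet the criteria for MOF" as an endpoint, along with failure by organ. SAP 8.1.2.2 compares both between arms by Fisher exact test in the safety population.

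**The concern.** SpO2 is a percentage and PaO2 is a pressure. Dividing each by FiO2 gives numbers on different scales, and the mm Hg label cannot be right for SpO2/FiO2. Footnote a calls the SpO2 route a modified score, but a reader of Table 14 has only the PaO2/FiO2 numbers to apply.

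Two separate errors follow. First, the 100% ceiling on saturation means that at higher FiO2 the score depends on how much oxygen is given and not on how well the subject oxygenates. Second, at lower FiO2 the shared cut-offs can leave a hypoxaemic subject below the organ-failure line.

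The EAC judges MOF against the criteria in the protocol, so it inherits the row as printed, and an event scored too low may never reach it. Protocol 2.5 ranks MOF with death as the worst outcomes of postoperative infection. The SAP expects few such events, so a handful of misclassified subjects could blur the comparison.

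**Working it through.** **Inputs from the documents:** the Table 14 cut-offs, and organ failure as a score of 3 or more. **Inputs not in the documents:** SpO2 cannot exceed 100%; room air is FiO2 0.21. There is no sponsor calculation to reproduce, because the cut-offs are definitions.

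**1. Ceiling.** The largest possible SpO2/FiO2 is 100/FiO2.

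| FiO2 | 100/FiO2 | Score at 100% saturation |
|---|---|---|
| 0.25 | 400 | 1 |
| 0.40 | 250 | 2 |
| 0.49 | 204 | 2 |
| 0.50 | 200 | 3 |
| 0.60 | 167 | 3 |
| 1.00 | 100 | 4 |

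From FiO2 0.50 upward no saturation gives less than score 3. From 0.25 upward score 0 is impossible.

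**2. Under-scoring.** Score 3 needs SpO2 ≤ 200 × FiO2.
- FiO2 0.40: the limit is 200 × 0.40 = 80%. SpO2 of 82% gives 82/0.40 = 205, score 2.
- Room air: score 1 needs SpO2 ≤ 400 × 0.21 = 84%. SpO2 of 85% gives 85/0.21 = 405, score 0.

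**3. Same patient, two routes.** This step needs an assumed oxyhaemoglobin dissociation curve, which is not in the documents: SpO2 = 100/(23400/(p³ + 150p) + 1), with p = PaO2 × 26.8/P50 and P50 from 24 to 30 mm Hg.

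| FiO2 | PaO2 (mm Hg) | PaO2/FiO2 (score) | SpO2 over the P50 range | SpO2/FiO2 (score) |
|---|---|---|---|---|
| 0.40 | 60 | 150 (3) | 87–93% | 218–232 (2) |
| 0.40 | 80 | 200 (3) | 94–97% | 235–242 (2) |
| 0.50 | 225 | 450 (0) | 99.7–99.9% | 199–200 (3) |

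The examples in step 2 can be read against this curve.
- At FiO2 0.40, SpO2 of 82% is below the 87% found at PaO2 60, so PaO2 is under 60 and PaO2/FiO2 is under 150. That is at least score 3 by PaO2 and score 2 by SpO2.
- On room air, SpO2 is 71–83% at PaO2 42 and 89–94% at PaO2 63. SpO2 of 85% therefore implies PaO2/FiO2 between 42/0.21 = 200 and 63/0.21 = 300. That is score 2 by PaO2 and 0 by SpO2: dysfunction is lost, but not an organ failure.

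**4. The two errors have different causes.** For a score 3 cut-off of c, full saturation meets it once FiO2 ≥ 100/c. Any c of 200 or more therefore keeps the over-count, and raising c lowers the FiO2 at which it starts. Raising c would, however, reduce the misses in steps 2 and 3. New cut-offs alone need not cure both.

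**The case against.** The strongest reply is that the SpO2 route is narrow and well guarded.
- It applies only without a PaO2 and with a directly measured FiO2. Scores 3 and 4 are tied to respiratory support.
- Daily scoring begins once organ dysfunction has been identified (Protocol 6.3.1.2.1, 6.4.3), so oxygen given to a well subject does not by itself start it.
- MOF needs a second failing organ, and the EAC is blinded.
- SAP 8.1.2.2 already urges caution with the organ-system p-values and expects sparse MOF.
- The SRM and reference 58 may hold the correct scoring.

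Most of this stands as a limit on reach. A reader might infer that anyone on FiO2 of 0.5 or more is counted as organ failure. The documents do not support that: with a PaO2 of 225 mm Hg at FiO2 0.50 the ratio is 450, score 0, and it is unclear whether a face mask counts as respiratory support. Nor do they show that the SpO2 route is common, that MOF is the key safety signal (it is not a listed primary safety endpoint), or that the error favours one arm.

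What the reply does not remove is the rule itself. Within its conditions the printed row still gives the scores shown. If the SRM differs, the two conflict. Five cut-offs under five score columns look complete, though a row lost in text extraction cannot be fully excluded.

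**Conclusion.** The concern holds in limited form. Table 14 as printed puts two different ratios on one scale. For subjects who meet the SpO2 conditions, FiO2 of 0.50 or more forces a score of at least 3. At lower FiO2, some hypoxaemic subjects fall short of the score they would get from PaO2.

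The ceiling is plain arithmetic. The comparison between routes rests on the assumed curve but gives the same scores in all three tabulated cases across P50 of 24 to 30 mm Hg. The number of subjects affected cannot be estimated, because the documents do not say how often SpO2 would be used.

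The consequence is added misclassification in the respiratory organ-failure and MOF safety comparisons. Because scoring is blinded it is likely to be similar in both arms, so the expected harm is lost clarity in sparse data and not a directional bias. Primary efficacy is unaffected. The point is worth correcting but does not threaten the trial's main conclusion.

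**What to change.** 1. Restrict the printed cut-offs and the mm Hg unit to PaO2/FiO2.
2. Give SpO2/FiO2 its own unit-free row that reproduces the modified score the protocol already cites, including any limit that score sets on use near full saturation. No cut-off is proposed here.
3. Reconcile the row with footnotes a and b, define respiratory support, and align the SRM.
4. Before the MOF analysis, re-check SpO2-based respiratory scores blinded. The documents do not show that raw SpO2 and FiO2 values are in the CRF: scores go on a worksheet and enter the CRF only once an organ reaches 3. The check may therefore need worksheets or source records, above all for events scored too low.
5. If the cited score does not remove the ceiling problem, report organ-failure and MOF results with and without SpO2-based respiratory scores.

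The cost is a table edit, some source review, and possible blinded re-adjudication of a few events. No new subject procedures are needed.

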7.2.3.1. Assessment of Deaths

Any deaths that occur during the study will be assessed by the EAC for potential relationship to a PDI and/or association with *S aureus*. The DMC will also review deaths during scheduled safety data review meetings, or on an ad hoc basis if required, in accordance with the DMC charter.

Any death that occurs from the day of informed consent to 180 days after surgery will be reported in the CRF and to the sponsor. Any death that occurs from the date of informed consent will be reported as an SAE.

7.2.4. Pregnancy Testing

For female subjects of childbearing potential, a urine or serum pregnancy test, with sensitivity of at least 25 mIU/mL, will be performed immediately before administration of the vaccine/placebo. A negative pregnancy test result is required before the subject may receive the investigational product. After randomization and vaccination, if the subject becomes pregnant during the study, the subject may continue to participate in the study as it remains appropriate to follow a subject who becomes pregnant for the development of postoperative PDI and fetal outcome. Pregnancy tests may be repeated at the request of IRBs/independent ethics committees (IECs) or if required by local regulations.

7.3. Microbiology Assessments

7.3.1. Microbiological Laboratory Procedures

All samples for microbial culture from suspected infections, regardless of the source of the culture material, will be sent to the local microbiology laboratory for isolation of any organisms. Samples for microbiological cultures will be collected as outlined in the study procedure and reference manual. Each pathogen isolated should be identified to the genus and species level, if possible. *S aureus* strains will be tested for methicillin sensitivity.

At the investigational site laboratory, study site personnel are responsible for obtaining all *S aureus* isolates and sending them to the central laboratory for processing and shipment of samples to the sponsor.

If the investigational site laboratory subcontracts with an outside laboratory, study site personnel are responsible for obtaining all *S aureus* isolates from the outside laboratory and sending them to the central laboratory for processing and shipment of samples to the sponsor.

The local or outside microbiology laboratory is expected to retain a duplicate of each isolate (eg, stored at -70°C) until the isolate has been received, tested, and reported by the central laboratory.

The central laboratory will coordinate and provide each study site with shipping supplies and detailed instructions for the shipment and storage of all microbiological isolates. In addition to species verification, *S aureus* cultures may be further evaluated for genotypic and possibly phenotypic markers by the central laboratory.

Sample collection, storage, and shipping information can be found in the laboratory manual.

7.3.2. Blood Cultures

For all suspected BSI, deep incisional SSI, and organ/space SSI, and where clinically indicated for superficial SSI, 2 sets of blood cultures should be obtained and timed according to the local institution's policy using different sampling sites. Anaerobic and aerobic samples should be collected. The timing of the repeat culture(s) is at the discretion of the investigator. Whenever possible, blood should be collected from peripheral veins; blood drawn through an intravascular catheter will be specifically identified as such in the CRF. *S aureus* isolates will be processed as described above.

7.3.3. Operative (Surgical Site) Wound Cultures

Throughout the subject's participation, bacterial cultures will be obtained at any point during the study if the subject undergoes any drainage procedure. Aerobic and anaerobic cultures will be taken from the site of suspected infection during surgical procedures.

